Study Protocol and Analytic Plan

Title: Impact of Front-of-Package Labels on Weight Bias Among Latines

Date: April 29th 2024

NCT #: NCT06293937

Introduction

The goal of the analysis described in this document is to use data to be collected through an online experiment with a sample of Latine and low English proficiency adults to examine the effects on explicit weight bias of a selection task using 4 different types of front-of-package food labels. This document pre-specifies our planned analytic approach prior to data collection.

Study Protocol

Participants will complete an online randomized experiment programmed in Qualtrics. After providing informed consent, participants will be randomly assigned to view 1 of 4 types of front-of-package nutrient labels during a product selection task: numerical label, interpretive text-only label, interpretive label containing a magnifying glass icon, or separated interpretive labels containing a magnifying glass icon. Participants will first view their assigned label on 3 sets of products (with 3 products per set) and select the product they believe is most and least healthy and the product they most want to purchase. After this selection task, participants will answer questions measuring explicit weight bias and attribution of personal responsibility of body weight.

Hypotheses

Explicit weight bias (primary outcome): We hypothesize that there will be no difference in weight bias between participants in the 4 arms (H1).

Attribution of personal responsibility for body weight (secondary outcome): We hypothesize that there will be no difference in attribution of personal responsibility for body weight between participants in the 4 arms (H2).

Main Analyses

We will use a two-sided critical alpha of 0.05 to conduct all statistical tests. All confidence intervals presented will use a 95% confidence level. Analyses of the primary and secondary outcomes will include all participants according to the trial arm to which they were randomized.

To prepare the data, we will verify that Cronbach's alpha for the explicit weight bias scale is sufficient (≥ 0.7) and, if so, we will average items to create a mean score on this scale for each participant. If Cronbach's alpha is not sufficient (< 0.7), we will drop items as necessary to improve reliability or treat items as separate constructs. We will also examine the Spearman Brown coefficient for the two-item scale used to measure attribution of personal responsibility for body weight and create a mean score on this scale for each participant.

We will descriptively report unadjusted means for the primary and secondary outcomes for each experimental arm. To test H1 and H2, we will fit separate linear regression models including indicator variables for label type and specifying the numerical label as the referent type. We will additionally use these models to estimate the effects of text-only vs. magnifying glass, text-only vs. exclamation point, and magnifying glass vs. exclamation point. We will not adjust the p-value for each label type compared to the numerical label, but will adjust for multiple tests for the three additional pairwise comparisons using the Bonferroni-Holm correction.

Exploratory Analyses

We may examine how demographic characteristics (i.e., gender, age, race, education, English proficiency, percentage of life spent in the US, and perceived weight status) correlate to weight bias among participants. We will fit a linear model including these characteristics as independent variables. If the main analysis reveals a significant effect of the experimental arms on explicit weight bias, we will also include label type in the model as an independent variable.

Sample Size and Power

This study will follow a parent study examining the effects of a selection task using the aforementioned label types on participants' desire to purchase and ability to identify the healthiest product in each product set. The total sample size (~4,000 participants) was calculated based on the primary outcomes of the parent study.

Using G*Power3.1 (ANOVA: fixed effects, omnibus, one-way) we determined the minimum effect size we would be able to detect on our primary outcome with this pre-determined sample size. With 80% power, a critical alpha of 0.05, and 4 groups, we would be able to detect an effect of $f=0.066$ (equivalent to $d=0.13$). Given that a previous study to analyze the effect of FOPs on weight bias obtained an effect size of $d=0.16$ comparing warning labels to control labels, this study's sample should be sufficiently large to detect similar effects.

Interim Analysis

No interim analyses are planned.

Exclusions and Outliers

We will exclude participants who complete the survey implausibly quickly (defined as <1/3 of the median completion time). We will exclude participants who complete less than 90% of the survey.

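### The primary weight-bias model is valid but uses label indicators only; naming a covariate-adjusted model in advance is a cheap, small gain in precision

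*Combined protocol and SAP*

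**What the plan says.** Main Analyses, on the models for both hypotheses: "we will fit separate linear regression models including indicator variables for label type and specifying the numerical label as the referent type". No other model term is named, so a label-only model is the fair reading. The same section states that "Analyses of the primary and secondary outcomes will include all participants according to the trial arm to which they were randomized".

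Under Exploratory Analyses, the plan offers an optional model that relates participant characteristics to weight bias: "We may examine how demographic characteristics (i.e., gender, age, race, education, English proficiency, percentage of life spent in the US, and perceived weight status". If the main analysis finds a significant effect of arm on weight bias, "we will also include label type in the model as an independent variable". An adjusted label effect is therefore planned only after a significant unadjusted result, and only for weight bias.

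Hypotheses: for the primary outcome, "We hypothesize that there will be no difference in weight bias between participants in the 4 arms". H2 makes the same prediction for attribution of personal responsibility.

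Study Protocol: "After this selection task, participants will answer questions measuring explicit weight bias and attribution of personal responsibility of body weight". The documents do not say when the seven demographic characteristics are asked.

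**The concern.** Covariates that predict the outcome reduce residual variance and narrow the confidence interval for a randomized comparison. The plan names seven candidates for weight bias but uses none of them in the analysis that tests H1. Because H1 predicts no difference, readers will look closely at the width of the intervals. Under that predicted result no adjusted label effect is planned at all, and any adjusted estimate that does appear will have been triggered by a significant unadjusted one. Naming the governing model now would remove that dependence and collect whatever precision the covariates offer.

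The stake is modest: a slightly narrower interval and a model choice settled in advance. The validity of the H1 test is not in question.

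**Working it through.** **The plan's own figure.** Sample Size and Power gives a minimum detectable f=0.066 (d=0.13) for a one-way omnibus ANOVA with 4 groups, about 4,000 participants, alpha 0.05 and 80% power. With a noncentral F on 3 and 3,996 degrees of freedom and noncentrality N·f², 80% power at N=4,000 corresponds to f=0.052 (2f=0.104). Power at f=0.066 is 95.3%. The stated figure fits 95% power (f=0.0656), not 80%. That mismatch is conservative, is a separate matter, and is not used below.

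**Inputs from the documents.** About 4,000 participants, 4 arms, two-sided alpha 0.05, and d=0.16 from the passage noting that "a previous study to analyze the effect of FOPs on weight bias obtained an effect size of" that size for warning versus control labels.

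**Assumed inputs.** Equal arms (1,000 each); outcome SD of 1; k=20 covariate terms; R-squared of 0 to 10%; the d=0.16 applied to a comparison with the numerical label.

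**Formulas.**
- Unadjusted SE = √(2/n) = √(2/1,000) = 0.04472.
- Adjusted SE = √(2/n) × √(1−R²) × √(1 + k/(4n−k−5)). With n=1,000 and k=20, the last factor is √(1 + 20/3,975) = 1.0025.
- Half-width = t(0.975) × SE. Power from the noncentral t with noncentrality 0.16/SE.

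| Model | SE | Ratio | 95% half-width (SD) | d at 80% power | Power at d=0.16 |
|---|---|---|---|---|---|
| Label only | 0.04472 | 1 | 0.0877 | 0.1253 | 94.70% |
| Adjusted, R²=0 | 0.04483 | 1.0025 | 0.0879 | 0.1256 | 94.61% |
| R²=1% | 0.04461 | 0.9975 | 0.0875 | 0.1250 | 94.80% |
| R²=2% | 0.04438 | 0.9924 | 0.0870 | 0.1244 | 94.99% |
| R²=5% | 0.04370 | 0.9771 | 0.0857 | 0.1225 | 95.55% |
| R²=10% | 0.04253 | 0.9511 | 0.0834 | 0.1192 | 96.41% |

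Simulation (500 runs, normal covariates) gave ratios of 1.0026, 0.9926, 0.9773 and 0.9511 at R² of 0, 2, 5 and 10%.

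**After exclusions.** If exclusions left 900 per arm (an assumed 10% loss), the label-only half-width is 0.0924 and power 92.4%. At R² of 1, 2, 5 and 10% the half-widths are 0.0922, 0.0918, 0.0903 and 0.0879, and power is 92.5%, 92.8%, 93.5% and 94.6%.

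**Break-even.** Adjustment pays when R² exceeds 1 − 1/(1 + k/(4n−k−5)). At n=1,000 this is 0.25% for k=10, 0.50% for k=20 and 0.75% for k=30.

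**Missing covariates.** If the items come after the task, whether they are answered is a post-randomization event. With a missing category, the shift is about −(outcome gap) × (arm difference in missingness). For an assumed 0.5 SD gap and a 1-point difference it is −0.5 × 0.01 = −0.005 SD. A simulation (3,000 runs, 3% base missingness) gave −0.004. The half-width gains at 1,000 per arm are 0.0002, 0.0007, 0.0020 and 0.0043 SD at R² of 1, 2, 5 and 10%. The −0.005 shift is larger in size than all four; the simulated value is larger than all but the last.

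**The case against.** The strongest reply is that there is no defect to correct. A prespecified unadjusted model in a randomized experiment of about 4,000 is a legitimate choice, and it matches the covariate-free power calculation. At R-squared of 1% to 2% the interval narrows by only 0.0002 to 0.0007 SD. No R-squared is documented, and the plan treats the link between demographics and weight bias as an open question. A missing-category rule could introduce a shift larger than the gain, and reporting missingness by arm would reveal that shift without removing it.

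Most of this stands, and it limits the point without defeating it. The shift needs missingness that differs by arm, which is only assumed, and it would have to arise among those left after the rule "We will exclude participants who complete less than 90% of the survey". The cost if the covariates explain nothing is an SE about 0.25% higher.

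A reader might infer four stronger claims that the documents do not support:
- That the label-only model is biased or wrong. Randomization makes it valid.
- That the trial needs adjustment for adequate power. Power at d=0.16 is already about 95% with 1,000 per arm.
- That H2 would gain in the same way. The exploratory model concerns weight bias only, and nothing links these variables to the H2 outcome.
- That narrower intervals would confirm no difference. The plan states no equivalence margin, and a non-significant result is not by itself evidence of no difference, with or without covariates.

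**Conclusion.** The point holds as an optional, low-cost improvement to the H1 analysis. Over an assumed R-squared of 1% to 10%, adjustment cuts the SE by 0.3% to 4.9% and adds 0.1 to 1.7 percentage points of power at d=0.16 (94.70% to between 94.80% and 96.41%). Below a break-even R-squared of about 0.5% it costs a little precision. These figures rest on equal arms of 1,000, 20 covariate terms and an R-squared that the documents do not supply, so confidence in the size of the gain is moderate.

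Five of the seven characteristics (gender, age, race, education, share of life lived in the US) have true values that a label cannot alter. Answers on English proficiency and perceived weight status could shift after the task, so their use depends on timing.

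**What to change.** Before data collection, amend Main Analyses as follows:
- Name as the primary H1 model the linear regression with label indicators plus gender, age, race, education and share of life lived in the US, with the coding of each fixed.
- Report the label-only model as a sensitivity analysis, and state that the adjusted model governs if the two disagree.
- State when each characteristic is asked. Include English proficiency and perceived weight status only if they precede the label task.
- Fix one rule for missing covariate values, such as a missing category, that drops nobody who remains after the stated exclusions. If the items follow the task, also report covariate missingness by arm.
- Leave H2 unadjusted, or adjust it for consistency only; either is acceptable.

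The cost is a few sentences, about 20 degrees of freedom out of about 4,000, and slightly longer reporting. No new data are needed. Once data are in hand, changing the primary model would be post hoc, and this change should not then be made.

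### Free improvement: Shaffer's step-down rule can replace Bonferroni-Holm for the three extra pairwise contrasts, adding about 4 points of per-contrast power at d=0.13 within the same 5% familywise limit

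*Combined protocol and SAP*

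**What the plan says.** The Study Protocol section has participants "randomly assigned to view 1 of 4 types of front-of-package nutrient labels during a product selection task". The Main Analyses section fits one linear regression per outcome with the numerical label as referent. From the same models it also estimates "text-only vs. magnifying glass, text-only vs. exclamation point, and magnifying glass vs. exclamation point".

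The two sets of contrasts are treated differently. For the comparisons with the referent: "We will not adjust the p-value for each label type compared to the numerical label". For the other three, the plan "will adjust for multiple tests for the three additional pairwise comparisons using the Bonferroni-Holm correction". The overall level is given as: "We will use a two-sided critical alpha of 0.05 to conduct all statistical tests".

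The only power statement, under Sample Size and Power, is for a four-group omnibus ANOVA. No power or effect size is given for the three adjusted contrasts.

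**The concern.** Holm's thresholds for three p-values are 0.05/3, 0.05/2 and 0.05. They are built for hypotheses that may be true or false in any combination. All the pairs among three means are not like that. If A and B differ, C cannot equal both, so exactly two true equalities is an impossible state. Holm's second threshold of 0.025 guards against that state.

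At stake is efficiency in the additional comparisons. When one interpretive format really differs from the other two, Holm will more often find one of the differences and miss the second than 5% familywise control requires. The sample size was fixed by the parent study, so the choice of procedure is one of the few ways left to gain power.

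**Working it through.** **Inputs.**
- Two-sided alpha 0.05 (Main Analyses).
- Four arms (Study Protocol) and about 4,000 participants (Sample Size and Power). The allocation ratio is not stated. Assuming equal arms, 4,000/4 = 1,000 per arm.
- Effects are standardised, so SD = 1.
- d=0.13 and d=0.16 come from Sample Size and Power and serve only as a scale. The first belongs to the four-group ANOVA, the second to warning labels against control labels. Neither describes one interpretive format against another.

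**The plan's own figure.** The plan states f=0.066, d=0.13 (d = 2f = 0.132), with the inputs "With 80% power, a critical alpha of 0.05, and 4 groups". Power was computed from the noncentral F with 3 and N−4 df and noncentrality N·f². At N=4,000, 80% power corresponds to f=0.052 (d = 2f = 0.10), and f=0.066 has 95.3% power. The stated figure is therefore not reproduced at 80%. That is a separate matter and does not affect this point, which depends only on n per arm and d.

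**Familywise control, by logic.** Among three means, the number of true equalities can only be three, one or none.
- Three true: an error requires the smallest p-value to fall below 0.05/3. By Bonferroni the probability is at most 3 × 0.05/3 = 0.05.
- One true: an error requires that single true-null p-value to fall below 0.05 at most, so the probability is at most 0.05.
- None true: no error is possible.

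Thresholds of 0.05/3, 0.05, 0.05 therefore control familywise error strongly at 5%. Each is at least as large as Holm's, so every Holm rejection is kept.

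**Thresholds in effect-size units.** The standard error of a difference is √(2/1,000) = 0.0447.
- 0.05/3: z = 2.394, observed difference 2.394 × 0.0447 = 0.107
- 0.05/2: z = 2.241, observed difference 0.100
- 0.05: z = 1.960, observed difference 0.088

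At the second step, Holm asks for 0.100 and Shaffer for 0.088.

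**Power, by simulation** of three normal arm means with two-sided z tests (400,000 to 2,000,000 replicates per case; repeat runs differ by about 0.1 point). One arm differs from the other two by d:

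| d | Per contrast, Holm → Shaffer | Both true differences, Holm → Shaffer | At least one rejection, either rule |
|---|---|---|---|
| 0.05 | 10.8% → 12.2% | – | – |
| 0.10 | – | 32.8% → 41.5% | 60.3% |
| 0.13 | 72.8% → 77.2% (+4.4) | 61.6% → 70.3% (+8.7) | 84.1% |
| 0.16 | 90.4% → 92.9% (+2.5) | 84.8% → 89.8% (+5.0) | 95.9% |

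Over a grid of d from 0.04 to 0.29, the largest gain in finding both true differences was at d=0.11: 42.3% to 51.6% (+9.2 before rounding).

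**Other patterns.** With means 0, 0.08, 0.16, each adjacent pair rises from about 35% to 42%, the extreme pair from 88.6% to 89.1%, and all three differences from 9.5% to 10.7%. The largest single-pair gain on the grid was 8.2 points (range 0.15, middle arm at 0.4 of it).

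**Fewer analysed.** With 900 per arm and d=0.13, the chance of finding both true differences rises from 55.2% to 64.3% (+9.1).

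**Familywise error.** Under the full null it is 4.4% for both rules. With one true equality at d=0.13 it is 3.3% for Holm and 4.9% for Shaffer. Across the one-equality cases Shaffer reaches about 5.0%.

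**The case against.** **Holm is valid and pre-specified, so nothing is wrong.** This stands. The plan makes no error here. It leaves available power unused, and only in the additional comparisons. The contrasts with the numerical label are untouched.

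**A reader might infer that Holm tilts the trial toward its predicted result of no difference.** The plan does not support that. Both rules test the smallest p-value at 0.05/3, so in any data set either both reject something or neither does. A conclusion of no difference anywhere in this family is equally likely under either rule. Shaffer can only add second and third rejections.

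**A reader might take 9 points as the general loss of power.** It is a ceiling for one measure, declaring both true differences, in one pattern, near d=0.11. Per contrast the gain is about 4 points at d=0.13 and 2.5 at d=0.16, and it shrinks at small effects (1.4 points at d=0.05).

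**Holm's stricter step lowers false positives.** True: 3.3% against 4.9% at d=0.13. Shaffer spends allowance that the plan's 5% level already permits.

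**Another procedure gains more.** A closed test gated by a three-arm F test raises the chance of finding both true differences from 61.6% to 72.1% (+10.5) at d=0.13, also within 5%. But it need not keep every Holm rejection. With the middle arm midway, the test statistic equals the square of the largest pair's z, so z = 2.394 gives 2.394² = 5.73. That falls below the 5% chi-square critical value on 2 df, 5.99. Shaffer's rule is the simpler change because it loses none of Holm's findings.

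**Conclusion.** The point holds as an optional, cost-free gain in efficiency. Replacing Holm by Shaffer's rule leaves the chance of any finding unchanged and improves the identification of which formats differ. The gain is about 4 points per contrast at d=0.13, 8.7 points for finding both true differences at that d, and about 9 at most.

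That Shaffer dominates Holm, and that familywise error stays at or below 5%, follow from logic. The sizes rest on equal arms of about 1,000, normal-theory tests and one arm differing from the other two. The plan states neither the allocation nor the expected exclusions, and no effect for these pairs, so the d values are illustrative.

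One condition applies. The Study Protocol section describes the fourth arm as separated labels with a magnifying glass icon, while Main Analyses names an exclamation point. The three contrasts are all the pairs among the non-numerical arms only if these are the same arm.

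**What to change.** In Main Analyses, replace the reference to Bonferroni-Holm with wording such as: *Shaffer's step-down modification of Holm for all pairs among three arms: the smallest p-value is compared with 0.05/3 and, if rejected, the other two are compared in order with 0.05.*

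With p(1) ≤ p(2) ≤ p(3), the adjusted p-values, each capped at 1, are:
- first: 3·p(1)
- second: max(3·p(1), p(2))
- third: the larger of the second adjusted value and p(3)

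Apply this in both the H1 and the H2 model. In the same edit, reconcile the name of the fourth arm between Study Protocol and Main Analyses.

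The cost is one sentence and a few lines of code. No participants are added, no Holm rejection is lost, and familywise error stays within 5%. The change should be made before data collection, the point at which the document says it fixes the analysis.

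### The stated detectable effect, f=0.066 at 80% power, does not follow from its inputs: 0.066 matches 95% power, the 80% figure is 0.052, and the conversion to d=0.13 assumes an unstated pattern of arm means

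*Combined protocol and SAP*

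**What the plan says.** The sample size was not set for this study: "The total sample size (~4,000 participants) was calculated based on the primary outcomes of the parent study". The plan then reports what that number can detect. On the method it says: "Using G*Power3.1 (ANOVA: fixed effects, omnibus, one-way) we determined the minimum effect size we would be able to detect on our primary outcome". The result is given as: "With 80% power, a critical alpha of 0.05, and 4 groups, we would be able to detect an effect of $f=0.066$ (equivalent to $d=0.13". That d is set beside d=0.16, which an earlier study found for warning labels against control labels, and the section concludes that "this study's sample should be sufficiently large to detect similar effects".

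The Main Analyses section does not describe an omnibus test. It fits a linear regression with label indicators, compares each of three labels with the numerical label without adjustment, and makes three further pairwise comparisons with a Bonferroni-Holm correction. On alpha it states: "We will use a two-sided critical alpha of 0.05 to conduct all statistical tests". The Exclusions and Outliers section removes very fast responders and participants with less than 90% of the survey completed. It gives no expected rate, and the power statement makes no allowance for exclusions.

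**The concern.** A sensitivity calculation of this kind has four inputs (N, number of groups, alpha, power) and one output (f). All four inputs are given, so the output can be checked, and 0.066 looks too large for 80% power at N=4,000.

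The conversion to d raises a second question. Cohen's f describes the spread of all four means, whereas d describes one pair. The two are linked by a fixed factor only once the pattern of means is specified, and the plan specifies none. The plan nevertheless compares the converted d directly with a pairwise d from another study.

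Both hypotheses predict no difference between arms, so the expected result is a null one. Readers will use this paragraph to judge how informative a null is, and it is the only sensitivity statement for the primary outcome.

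**Working it through.** **Inputs**
- N=4,000, 4 groups, alpha 0.05, power 80%, one-way fixed-effects omnibus F test (Sample Size and Power).
- Equal allocation, 1,000 per arm. This is an assumption: the plan randomises to four label types but gives no ratio.

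**Step 1. The plan's own figure.** Power is the upper tail of a noncentral F beyond the central 5% critical value, with df1 = 4 − 1 = 3, df2 = 4,000 − 4 = 3,996 and noncentrality λ = N·f².

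| Power | Detectable f at N=4,000 |
|---|---|
| 80% | 0.0522 |
| 90% | 0.0596 |
| 95% | 0.0655 (rounds to 0.066) |

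At f=0.066, λ = 4,000 × 0.066² = 17.4 and power is 95.3%. At f=0.0522, λ = 10.9, which gives 80%. The stated f exceeds the 80% figure by 0.066/0.0522 − 1 = 26%.

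Solving for N at f=0.066 gives about 2,507 for 80% power and about 3,946 for 95%. Only the second fits a total of about 4,000.

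**Step 2. Can another reading give 0.066 at 80% power?**
- N from 3,400 to 4,400: f runs from 0.057 to 0.050.
- Alpha 0.025: 0.057. Alpha 0.05/6: 0.063.
- 2, 3 or 5 groups: 0.044, 0.049, 0.055.

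None does.

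**Step 3. From f to d.** For equal arms, f² is the variance of the four means (divisor 4) over the within-arm variance. Let d be the largest pairwise difference in SD units.
- Two arms at each extreme: variance d²/4, so d = 2f.
- One arm apart from three: variance 3d²/16, so d = 4f/√3 = 2.31f.
- Two arms at the extremes and two midway: variance d²/8, so d = √8·f = 2.83f.

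| Pattern | d at f=0.066 | d at f=0.0522 | Omnibus power at d=0.13 | Omnibus power at d=0.16 |
|---|---|---|---|---|
| Two and two | 0.132 | 0.104 | 94.6% | 99% |
| One against three | 0.152 | 0.121 | 86.1% | 97% |
| Two extremes, two midway | 0.187 | 0.148 | 68.0% | 86% |

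The plan's 0.13 is 2 × 0.066 = 0.132, the first row only.

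**Step 4. The tests actually planned.** For one pair with n per arm, the detectable d at 80% power is (z for two-sided alpha + 0.8416) × √(2/n).
- n=1,000, alpha 0.05: (1.960 + 0.8416) × 0.04472 = 0.125.
- n=1,000, alpha 0.05/3 (first Holm step): (2.394 + 0.8416) × 0.04472 = 0.145.
- n=900 (10% exclusions, an assumed rate): multiply both by √(1,000/900) = 1.054, giving 0.132 and 0.153.

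**The case against.** The best defence is that nothing important rests on the number. The error in f is conservative: the omnibus test is more sensitive than the plan claims. The sample size comes from the parent study and would not move. The section's one conclusion also survives. At d=0.16 omnibus power is 86% to 99% by pattern. Pairwise power at 1,000 per arm is about 95% at alpha 0.05 and 88% at alpha 0.05/3; at an assumed 900 per arm it is 92% and 84%. The d of 0.13 happens to lie close to the right answer for the unadjusted contrasts with the numerical label (0.125, or 0.132 at 900 per arm). A null result will in any case be read mainly from the planned 95% confidence intervals.

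All of this is true, and it limits the consequence. It does not make the statement correct. The plan presents f=0.066 as the minimum detectable effect at 80% power, so reading it as at least 80% does not help. The near-agreement on d is a coincidence of a different test, one that the power paragraph does not mention. The 2f conversion is valid for a two-and-two split, so the fault there is an unstated assumption rather than an impossible formula. The Holm-adjusted contrasts have a detectable d above 0.13, and the plan reports no figure for them.

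**Conclusion.** The point holds. With the plan's own inputs the detectable effect at 80% power is f=0.052. The stated f=0.066 has 95.3% power, so the power and effect size given together cannot both be right. That a 95% setting was used is inferred from the numerical match; the document does not say so.

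The statement that f=0.066 is "equivalent to $d=0.13" is true for only one arrangement of four means. For the planned pairwise tests the detectable d at 80% power is 0.125 unadjusted and 0.145 at the first Holm step.

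These figures assume equal arms and, unless stated otherwise, no loss to exclusions. The trial is not underpowered for d=0.16, and the design is unaffected. This is a definite error in the only reported sensitivity figure and should be corrected.

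**What to change.** In the Sample Size and Power section:

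1. Report either f=0.052 at 80% power or f=0.066 at 95% power, and state the N and the allocation ratio used.
2. Remove the equivalence to d=0.13.
3. Give the detectable d at 80% power for the planned tests: about 0.125 for each label against the numerical label (alpha 0.05) and about 0.145 for the further comparisons at the first Holm step, both at 1,000 per arm. Set these beside the earlier study's d=0.16.
4. Repeat the figures after the expected exclusions, with the assumed rate stated. At 10% they are about 0.132 and 0.153, and the omnibus f at 80% power is 0.055 (N=3,600).

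The cost is rewording one paragraph. Sample size, arms, tests and data collection do not change.
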